## Baseline Assessment

### Identifying measurable disease:

*Non-nodal tumor lesions:* Measurable lesions are those that can be accurately measured in at least one dimension (longest diameter to be recorded) with a minimum size of:

- 10 mm by CT scan (CT scan slice thickness no greater than 5 mm) or MRI. If scans with slice thickness greater than 5mm are used, the minimum size should be twice the slice thickness.
- 20 mm by chest x-ray
- 10 mm caliper measurement by clinical examination (lesions which cannot be accurately measured with calipers should be recorded as non-measurable)
- For lesions within the liver parenchyma, only the portion of the lesion that shows typical HCC enhancement should be included in the measurement.

*Malignant lymph nodes:* To be considered pathologically enlarged, a lymph node must be  $\geq$  10 mm in short axis when assessed by CT scan (except nodes in the porta hepatis – see below). To be considered measurable, a lymph node must be  $\geq$  15 mm in short axis when assessed by CT scan.

*Lytic bone lesions or mixed lytic-blastic lesions,* with identifiable soft tissue components that can be evaluated by CT or MRI, can be considered as measurable lesions if the soft tissue component meets the definition of measurability.

Tumor lesions situated in a previously irradiated area are not considered measurable unless there has been demonstrated progression in the lesion.

### Identifying non-measurable disease:

All other lesions (or sites of disease), including small lesions (longest diameter <10 mm or pathological lymph nodes with short axis 10-14 mm) are considered non-measurable disease. Leptomeningeal disease, ascites, pleural/pericardial effusions, lymphangitic involvement of skin or lung, inflammatory breast disease, abdominal masses/ abdominal organomegaly identified by physical examination that is not measurable by reproducible imaging techniques and blastic bone lesions are all non-measurable.

*Intrahepatic lesions:* For lesions in the liver parenchyma, those that show typical HCC enhancement with longest diameter <10 mm, as well as those that show typical enhancement in a complex pattern that does not lend itself to reproducible measurement are considered non-measurable.

Porta hepatis lymph nodes: Lymph nodes detected at the porta hepatis can be considered malignant, but not measurable, if the lymph node short axis is at least 2 cm. Nodes in the porta hepatis are never considered measurable.

Portal vein thrombosis: Malignant portal vein thrombosis should be considered a non-measurable lesion.

### **Selection of target and non-target lesions:**

At baseline, lesions are divided into those that will be followed quantitatively (target lesions) and those that will be followed qualitatively (non-target lesions).

All measurable lesions up to a maximum of 2 lesions per organ and 5 lesions in total, representative of all involved organs should be identified as *target lesions* and be recorded and measured at baseline. These 5 lesions should be selected on the basis of their size (lesion with the longest diameter), be representative of all involved organs and should be suitable for reproducible repeated measurements. For the purposes of this selection, paired organs (such as the lungs) should be regarded as a single organ, and all lymph nodes should be regarded as a single organ.

If measurable lesions are present in the liver parenchyma, they should always be selected as target lesions before any other lesions are chosen. Up to 2 liver lesions can be selected, just as with any other organ.

The sum of the diameters (longest diameter for non-nodal lesions, short axis for nodal lesions) for all target lesions will be calculated and reported as the baseline sum of diameters. The baseline sum of diameters will be used as the reference measurement when looking for evidence of objective response at later visits.

If there are more than five measurable lesions, those not selected as target lesions will be considered together with non-measurable disease as non-target lesions.

Non-target lesions include all non-measurable lesions, plus any measurable lesions over and above the 5 listed as target lesions. It is possible to record multiple non-target lesions involving the same organ as a single item on the case record form (e.g.; ‘multiple enlarged pelvic lymph nodes’ or ‘multiple liver metastases’).

### **Post-baseline assessment**

At every visit after baseline, the investigator will assess the target lesions selected at baseline quantitatively (as described below), assess the non-target lesions selected at baseline qualitatively, and search for new lesions. The lesion assessments are then combined into an assessment of the entire subject at that visit (called the visit response or the overall response).

#### Target lesion assessment

The investigator will measure each target lesion in the same manner as at baseline. Extrahepatic non-nodal lesions will be measured using their longest diameter. Malignant lymph nodes (excluding those in the porta hepatis, which can never be target lesions) will be measured in short axis diameter. Intrahepatic target lesions will be measured in the longest diameter that shows typical HCC enhancement (excluding areas of necrosis).

If a lesion decreases in size to the point where it is still present, but cannot be measured accurately, a default value of 5 mm should be recorded for its diameter. If a lesion has disappeared, a value of 0 mm should be recorded for its diameter. If a lesion has split into distinct fragments, the longest diameter of each fragment should be measured, and the diameters added together. If two lesions have merged, the longest diameter of the entire resulting lesion should be measured.

The sum of diameters will be calculated by adding all target lesion diameters. The sum of diameters is always compared to two reference points: the baseline sum of diameters, and the smallest sum of diameters seen during the trial (also called the nadir). The baseline may actually be the nadir, if there has been no reduction in the sum of diameters during the trial. The target lesion response is then classified as follows:

Target lesion response	
Complete response (CR)	Complete disappearance of target lesions outside the liver Complete disappearance of typical HCC enhancement from all target liver lesions All target lymph nodes <10 mm
Partial response (PR)	At least a 30% decrease in the sum of diameters from baseline
Progressive disease (PD)	At least a 20% increase in the sum of diameters from the smallest value seen during the trial (including baseline), with at least a 5 mm absolute increase in the sum
Stable disease (SD)	Neither enough shrinkage to qualify as PR, nor enough growth to qualify as PD
Non-evaluable (NE)	One or more target lesions not evaluated because of imaging issues, coverage, or change in imaging technique
Please note that when lymph nodes are included as target lesions, a CR may occur even when the sum of diameters is not zero, since a normal lymph node will have a diameter greater than zero but less than 10 mm.	

### Non-target lesion assessment

Non-target lesions are assessed as a whole. After examining each non-target lesion, the investigator will classify the non-target lesion response as follows:

Non-target lesion response	
Complete response (CR)	
Complete disappearance of non-target lesions outside the liver
 
Complete disappearance of typical HCC enhancement from all non-target liver lesions
 
All non-target lymph nodes <10 mm
 
Resolution of malignant portal vein thrombosis (if present)

Progressive disease (PD)	Unequivocal progression of non-target lesions as a whole
Non-CR/Non-PD	Non-target lesions still present, without unequivocal progression
Not all evaluated	One or more non-target lesions not evaluated because of imaging issues, coverage, or change in imaging technique

To achieve unequivocal progression in patients with measurable disease on the basis of the non-target disease, there must be an overall level of substantial worsening in non-target disease such that, even in presence of SD or PR in target disease, the overall tumor burden has increased sufficiently to merit discontinuation of therapy. A modest ‘increase’ in the size of one or more non-target lesions is usually not sufficient to qualify for unequivocal.

Cytopathologic confirmation of the neoplastic nature of any effusion that appears or worsens during treatment is required to declare PD.

### New lesions

Outside the liver, any new lesion that is considered unequivocally malignant is evidence of progression, with no minimum size requirement.

For lesions within the liver, a new lesion can be classified as HCC (and therefore evidence of progression) if its longest diameter is at least 1 cm and it shows typical HCC enhancement. A new lesion that is at least 1 cm without typical HCC enhancement can be diagnosed as HCC if it shows at least 1 cm growth in subsequent scans. A lesion that is smaller than 1cm in longest diameter is not considered a new lesion according to the rules of this protocol.

An individual radiological event will be adjudicated in retrospect as progression at the time it was first detected by imaging techniques, even if strict criteria were fulfilled only on subsequent radiological testing. This means that if a new lesion is not unequivocal at the time of initial detection, but later becomes unequivocal, the date of progression will be the date it was first detected.

### Visit response

The response of the target lesions, the response of the non-target lesions, and the presence or absence of new lesions are combined into the visit response for the entire subject at this visit, using the tables below.

### **Response for patients with target and non-target lesions**

Target Lesions	Non-Target Lesions	New Lesions	Overall Response	Best Response for this category also requires
CR	CR	No	CR	
CR	Non-CR/Non-PD	No	PR	
CR	Not evaluated	No	PR	
PR	Non-PD or not all evaluated	No	PR	
SD	Non-PD or not all evaluated	No	SD	documented at least 6 wk. from randomization
Not all evaluated	Non-PD	no	NE	
PD	Any	Yes or No	PD	
Any	PD	Yes or No	PD	
Any	Any	Yes	PD	
Subjects with a global deterioration of health status requiring discontinuation of treatment without objective evidence of disease progression at that time should be reported as “ symptomatic deterioration ”. Every effort should be made to document the objective progression even after discontinuation of treatment.				

## Response for patients with non-target lesions only

Non-Target Lesions	New Lesions	Overall Response
CR	No	CR
Non-CR/Non-PD	No	Non-CR/non-PD*
Not evaluated	No	NE
Unequivocal PD	Yes or No	PD
Any	Yes	PD
* Non-CR/non-PD is preferred over “stable disease” for non-target disease.		

The following text descriptions of the visit response are logically equivalent to the tables above.

*Complete Response (CR)*: Disappearance of all clinical and radiological evidence of tumor (both target and non-target). Any pathological lymph nodes (whether target or non-target) must have a reduction in short axis to < 10mm.

*Partial Response (PR)*: At least a 30% decrease in the sum of diameters of target lesions taking as reference the baseline sum, no unequivocal progression of existing non target lesions and no appearance of new lesions.

*Stable Disease (SD)*: Steady state of disease. Neither sufficient shrinkage to qualify for PR nor sufficient increase to qualify for PD, no unequivocal progression of existing non target lesions and no appearance of new lesions.

*Progressive Disease (PD)*: At least a 20% increase in the sum of diameters of target lesions from the smallest sum on study (this includes the baseline sum if that is the smallest on study). In addition to the relative increase of 20%, the sum must also demonstrate an absolute increase of at least 5 mm. Unequivocal progression of existing non target lesions or the appearance of one or more new lesions also constitute progressive disease. Ascites or pleural effusion will be recorded as disease progression only if proven malignant.

In the absence of measurable disease, the same general concepts apply as noted above.

Progression is assessed on the basis of intrahepatic and extrahepatic disease together. Either the growth of intrahepatic lesions with typical arterial enhancement, or the growth of

extrahepatic tumors, can indicate progression, if the sum of diameters (for target lesions) or the qualitatively assessed total tumor burden (for non-target lesions) indicates progression.

### **Best Response**

The best overall response is the best visit response recorded from the start of the study treatment until the end of treatment. If SD is the best response seen during the study, it must be maintained for at least 42 days after the start of treatment.

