- Progression-free survival (PFS) from initiation of sorafenib is defined as the time interval measured from the start date of sorafenib treatment to documented (radiological or clinical) progression or death, whichever comes first.
- Time to progression (TTP) from initiation of sorafenib is defined as the time interval from start date of sorafenib treatment to the date of documented progression. Patients without tumor progression at the end of the study will be censored at their last date of tumor evaluation.
- Duration of sorafenib treatment is defined as the time interval from start date of sorafenib treatment to the date of permanent discontinuation of sorafenib treatment (regardless of the reason for discontinuation including death).
- The tumor status at different visits response according to mRECIST will be evaluated according to the categories “Complete Response”, “Partial Response”, “Stable Disease”, “Clinical Progression”, “Radiological Progression”, and “Not evaluable at this visit”. The best overall response will be analyzed providing absolute and relative frequencies of the tumor status categories.
- Incidence of Treatment-emergent Adverse Events (TEAEs) – patients will be monitored for TEAEs using the NCI-CTCAE Version 4.03. Details on the collection, management and reporting of TEAEs can be found in section 11.

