### **9.3.9. Tumor assessment**

Patients will be assessed for response to TACE and tumor assessment preferably by mRECIST. In case that an assessment by mRECIST is not possible, because this is not routinely done at the site of the treating physician, also other evaluation criteria can be used. In any case the criteria used have to be documented along with the tumor evaluation and the physician should use the same criteria throughout all tumor evaluations of one patient.

TACE response to most recent TACE will be assessed within 12 weeks after TACE and recorded for each TACE.

Response evaluation will also be done compared to initial TACE. For patients treated with sorafenib, response evaluation compared to initiation of sorafenib will be added.

Tumor assessment will be made at physicians' discretion using CT scan or MRI or equivalent imaging exam, starting from initial TACE.

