#### **9.7.4. Analysis of primary outcome(s)**

The primary efficacy endpoint is Overall Survival (OS). It is defined in this study as the time (days) from time of TACE non-eligibility to death due to any cause. Patients lost to follow-up or alive at the end of the study will be censored at the last date known to be alive.

For statistical evaluation, two patient cohorts of special interest will be compared regarding the primary endpoint. These two cohorts are defined as:

- Cohort 1: Patients with early start of Sorafenib treatment. This cohort comprises all patients where the physician decides at the time of TACE non-eligibility to choose Sorafenib as the next treatment option (regardless of whether TACE treatment is continued or not).
- Cohort 2: Patients without early start of Sorafenib treatment. This cohort comprises all patients where the physician decides at the time of TACE non-eligibility not to choose Sorafenib as the next treatment option.

This cohort also includes patients with TACE non-eligibility for whom the decision to treat with Sorafenib is made at a later points in time, patients who are never treated with Sorafenib as well as patients for whom another systemic cancer treatment has been chosen by the physician either at time of TACE non-eligibility or at a later point in time.

According to the definition of the two cohorts, patients where no TACE non-eligibility occurred during the study do not qualify for this analysis. In addition, patients treated with Sorafenib or any other systemic anti-cancer treatment prior to time of TACE non-eligibility are excluded from this analysis. These groups will be described separately.

As part of the descriptive analysis, Kaplan-Meier (KM) estimates for OS will be displayed for the two patient cohorts of special interest.

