### **Response duration**

The duration of overall response is measured from the time measurement criteria are first met for CR/PR (whichever is first recorded) until the first date that recurrent or progressive disease is objectively documented (taking as reference for progressive disease the smallest measurements recorded on study).

The duration of overall complete response is measured from the time criteria are first met for CR until the first date that recurrent disease is objectively documented.

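### Best overall response in sorafenib patients runs to the end of treatment, so a response produced by a TACE given during sorafenib counts in the sorafenib response rate

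*Protocol*

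**What the plan says.** Annex 16.5, under Best Response, gives the rule: "The best overall response is the best visit response recorded from the start of the study treatment until the end of treatment". It adds that stable disease must last at least 42 days from treatment start to count as the best response. It does not say which treatment is meant.

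Section 9.1.2 lists best overall response among the endpoints specific to patients treated with sorafenib: "The best overall response will be analyzed providing absolute and relative frequencies of the tumor status categories". It sets no other window. In the same list, duration of sorafenib treatment runs "to the date of permanent discontinuation of sorafenib treatment", whatever the reason for stopping.

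Section 9.7.4 places patients in the early-sorafenib cohort "regardless of whether TACE treatment is continued or not".

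Section 9.3.9 sets the comparison points. "For patients treated with sorafenib, response evaluation compared to initiation of sorafenib will be added". In parallel, "TACE response to most recent TACE will be assessed within 12 weeks after TACE and recorded for each TACE".

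**The concern.** A window that runs to the end of treatment does no harm where progression ends treatment and no other anti-tumour therapy is given meanwhile. Neither condition holds here. Treatment follows routine practice, sorafenib ends only when it is permanently stopped, and TACE during sorafenib is expected.

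Tumour response from the start of sorafenib is a named secondary objective (section 8.2). Analyses are repeated by region (section 9.7.1), and secondary endpoints may be compared between the two cohorts (section 9.7.5). If TACE responses enter the sorafenib response rate, the rate will tend to be higher where the two treatments are combined more often. A difference between regions or cohorts could then reflect TACE use and be read as a difference in response to sorafenib.

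**Working it through.** The protocol states no response rate, so there is no figure to reproduce. The check has three parts: the text, the response rules applied to examples, and an illustration of size.

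**1. Does anything close the window earlier?**
- Best Response (16.5): ends at end of treatment.
- Section 9.1.2: no separate end for best overall response; sorafenib treatment ends at permanent discontinuation.
- Section 9.3.9: response is judged against sorafenib initiation, with no reset or stop when a TACE is given.
- Response duration (16.5): this does stop at progression, running "until the first date that recurrent or progressive disease is objectively documented". Best response has no such stop.

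**2. What do the response rules do after a TACE?** Under 16.5, intrahepatic target lesions are measured by their enhancing diameter without necrotic areas, and measurable liver lesions are chosen first as targets. Partial response is "At least a 30% decrease in the sum of diameters of target lesions taking as reference the baseline sum". Target-lesion progression needs a rise of at least 20% and at least 5 mm from the smallest sum. The sums below are invented and start at sorafenib initiation, with no new lesion and no non-target progression.

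Example A, TACE before progression: 100 mm, 95 mm, TACE, 65 mm.
- 95 mm: (100 − 95)/100 = 5% fall, stable disease.
- 65 mm: (100 − 65)/100 = 35% fall, partial response.

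Example B, TACE after target-lesion progression: 100 mm, 95 mm, 125 mm, TACE, 65 mm.
- 125 mm: (125 − 95)/95 = 32% and 30 mm rise, progression.
- 65 mm: 35% fall from baseline, partial response.

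In both, best overall response under the annex is partial response. Ending the window at the TACE (A), or at progression or the TACE (B), gives stable disease, provided the 42-day condition is met.

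Example B fails if progression came from a new lesion or from non-target lesions. The visit-response tables then score progression whatever the target lesions do, for as long as that finding stands.

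**3. How large could it be?** Let b be the response rate on sorafenib alone, t the share of sorafenib patients given a TACE during sorafenib, and r the probability that such a TACE produces a response against the sorafenib baseline. Treating these as independent:

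counted rate = b + (1 − b) × t × r

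All three inputs are assumptions; the protocol gives none of them.

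| b | t | r | Counted rate |
|---|---|---|---|
| 5% | 10% | 20% | 0.05 + 0.95 × 0.10 × 0.20 = 6.9% |
| 5% | 30% | 20% | 0.05 + 0.95 × 0.30 × 0.20 = 10.7% |
| 5% | 50% | 40% | 0.05 + 0.95 × 0.50 × 0.40 = 24.0% |
| 10% | 10% | 20% | 0.10 + 0.90 × 0.10 × 0.20 = 11.8% |
| 10% | 30% | 40% | 0.10 + 0.90 × 0.30 × 0.40 = 20.8% |
| 10% | 50% | 40% | 0.10 + 0.90 × 0.50 × 0.40 = 28.0% |

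**The case against.** **The annex sentence does not name sorafenib.** It belongs to a general mRECIST text that also refers to randomization, which this study does not have. That is correct: the protocol nowhere writes a window specifically for sorafenib. The link arises because section 9.1.2 uses best overall response for sorafenib patients and leaves the annex rule as the only one available. If study treatment were read to include TACE, as study drug does in section 11.2, the window would mix the two treatments further.

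**Section 9.7.1 leaves calculated variables to the SAP.** The SAP was not at hand and may narrow the window. But the annex gives a complete rule and does not defer, so a narrower SAP rule would depart from the protocol.

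**Response under real-life care, TACE included, is a legitimate description.** This stands. It is a reason to keep the unrestricted rate and label it, since on its own it cannot be read as response to sorafenib. Responses to each TACE and TACE dates are recorded, so the two can be separated at analysis.

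**Stronger readings to avoid.** A reader might infer that anyone who progresses on sorafenib and then responds to a TACE becomes a sorafenib responder. The visit-response rules do not support this where progression came from new or non-target lesions. A reader might also take one of the illustrated rates as the expected inflation. Nothing in the protocol supports a particular value: many of these patients will already have met TACE non-eligibility, which can include TACE failure, so a lower r is plausible. Section 9.3.9 also permits criteria other than mRECIST, and the enhancement mechanism does not carry over to all of those.

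**Conclusion.** The point holds. As written, a response produced by a TACE given during sorafenib is counted in the sorafenib response rate. The main route is a TACE given before any progression. After progression the route is open only for target-lesion progression without new lesions or non-target progression.

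The size is unknown. Across the assumed inputs (t from 10% to 50%, r from 20% to 40%) the counted rate is 6.9% to 24.0% for a base of 5%, and 11.8% to 28.0% for a base of 10%. These ranges show only that the effect need not be trivial.

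The endpoint is secondary and descriptive. The primary overall survival analysis, the cohort assignment and the power calculation do not depend on it.

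**What to change.** In Annex 16.5 (Best Response) and section 9.1.2:
- State that, for the sorafenib endpoint, study treatment means sorafenib.
- Take best overall response from sorafenib start to the earliest of first documented progression, the next TACE or other systemic anti-cancer therapy, or permanent sorafenib stop.
- Also report the unrestricted best response, separately for patients with and without TACE during sorafenib.

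This changes an endpoint definition only; patient treatment is untouched. It needs a sentence or two in each place and a matching line in the SAP. The necessary data are already collected: TACE dates and dates of other systemic treatment (section 9.3.10) and documented progression (section 9.3.2). Non-systemic HCC therapies other than TACE are recorded with concomitant medication, where the start date need only give the year (section 9.3.6), so they could not serve as an exact cut-off.

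The downside is that some later scans no longer count and the restricted response rate will be lower.
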